10.2.5 SAEs (Including Deaths) and Adverse Events Leading to Study Drug Discontinuation

Treatment-emergent SAEs (including deaths) and AEs leading to study drug discontinuation will be summarized by SOC and PT and in listing format.

A listing of pre-treatment SAEs with onset dates prior to the first dose of study drug will be provided.

10.2.6 Area of Safety Interest

Detailed information about the search criteria for areas of safety interest (ASIs) are provided in Appendix B.

The final list will be based on the most updated final version of risankizumab Product Safety Statistical Analysis Plan, which is consistent to the most updated risankizumab Risk Management Plan.

Tabular listings of selected area of safety interest will be provided.

10.3 Analysis of Laboratory Data

Data collected from central and local laboratories, including additional laboratory testing due to an SAE, will be used in all analyses, except for Baseline derivation where SAE-triggered laboratory assessments on or before the first dose of study drug will be excluded. The clinical laboratory tests defined in the protocol operations manual (e.g., hematology and clinical chemistry) will be summarized.

Mean change from Baseline to each applicable post-baseline visit will be summarized for selected laboratory variables. The following descriptive statistics will be presented by treatment groups: number of observations, Baseline mean, visit mean, mean change from Baseline and its standard error, and the 95% confidence interval of the mean change from Baseline.

[figure not shown]
In addition, laboratory parameters will be tabulated using shift tables from Baseline to minimum and maximum values in each period (Period A and Period B), categorized by the toxicity grade according to NCI CTCAE Version 4.03¹ of the laboratory used for each sample. A similar shift table will also be provided to summarize shifts from Baseline to the final post-baseline value in each period.

Laboratory abnormalities meeting CTC criteria grade 3 and 4 at least once in each period will be summarized.

Laboratory abnormalities will be evaluated based on Potentially Clinically Important (PCI) criteria (Appendix C). For each laboratory PCI criterion, the number and percentage of subjects who have a laboratory value meeting the criteria at least once in each period will be summarized. Listings will be provided to summarize subject-level laboratory data for subjects meeting PCI criteria.

In addition, the frequencies and percentages of subjects with post baseline liver specific function test values in ALT/SGPT, AST/SGOT, alkaline phosphatase, and total bilirubin that meet the following criteria will be summarized by treatment groups:

- ALT $\geq 3.0 \times ULN$
- ALT $\geq 5.0 \times ULN$
- ALT $\geq 10.0 \times ULN$
- ALT $\geq 20.0 \times ULN$
- AST $\geq 3.0 \times ULN$
- AST $\geq 5.0 \times ULN$
- AST $\geq 10.0 \times ULN$
- AST $\geq 20.0 \times ULN$
- Alkaline phosphatase $\geq 1.5 \times ULN$
- Total bilirubin $\geq 2.0 \times ULN$
- ALT and/or AST $> 3 \times$ ULN and TBL $\geq 2 \times$ ULN

A listing of potentially clinically important (PCI) liver function laboratory values will include all subjects who met any of the following four criteria:

- ALT \geq 3 × ULN, or
- AST \geq 3 × ULN, or
- Alkaline phosphatase $\geq 1.5 \times ULN$, or
- Total bilirubin $\geq 2 \times ULN$.

A listing of possible Hy's Law cases, defined as those who meet all of the following conditions will be provided.

- ALT of $> 3 \times ULN$ or AST of $> 3 \times ULN$,
- Total bilirubin $\geq 2 \times ULN$

10.4 Analysis of Vital Signs

Vital sign measurements of systolic and diastolic blood pressure will be summarized.

Change from baseline to each applicable post-baseline visit will be summarized for each vital sign variable. The following descriptive statistics will be presented by treatment groups: number of observations, Baseline mean, visit mean, mean change from Baseline and its standard error, and the 95% confidence interval of the mean change from Baseline.

Vital sign variables will be evaluated based on potentially clinically important (PCI) criteria (Appendix D). For each vital sign PCI criterion, the number and percentage of subjects who have a vital sign value meeting the criteria at least once in each period will be summarized. Listings will be provided to summarize subject-level vital sign data for subjects meeting PCI criteria.

10.5 Safety Subgroup Analyses

The number and percentage of subjects with treatment emergent hypersensitivity events or injection site reactions may also be summarized by anti-drug antibody (ADA) status

and/or by neutralizing antibody (NAb) status, once the corresponding ADA and NAb data are completed.

10.6 Other Safety Analyses

No other safety analyses.

11.0 Other Analyses

No other analyses.

12.0 Interim Analyses

12.1 Data Monitoring Committee

[figure not shown]
An external data monitoring committee (DMC) composed of persons independent of AbbVie and with relevant expertise in their field will review unblinded safety data from the ongoing study. The primary responsibility of the DMC will be to protect the safety of the subjects participating in this study.

A separate DMC charter describes the roles and responsibilities of the DMC members, frequency of data reviews, relevant data to be assessed, and general operations.

Since there are no efficacy analyses for early stopping, no alpha adjustment is needed.

13.0 Overall Type-I Error Control

For each risankizumab dose, the statistical comparisons for the primary efficacy variable and the ranked secondary variables will be carried out in the hierarchical order between the corresponding risankizumab dose and placebo, under a 2-sided significance level of 0.025. This means that for each risankizumab dose, statistically significant results for the comparison in the higher rank (primary, then ranked secondary variables) are necessary to initiate the testing of the next comparison in the lower rank. Since a step-down procedure is used, each comparison will be tested at a significance level of 0.025 and overall alpha level of 0.025 will be preserved for each risankizumab dose.

[figure not shown]

Therefore, the family-wised type-I error rate is controlled under a 2-sided significance level of 0.05.

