# 7 STATISTICAL METHODS & DETERMINATION OF SAMPLE SIZE

## 7.1 Statistical and Analytical Plans

---

The Primary Analysis will be conducted after all continuing subjects complete Week 16 and all data pertaining to Period A are cleaned. This will be the only and final analysis for efficacy in Period A. Study sites and subjects will remain blinded to their initial treatment assignment for the duration of the entire study.

The statistical analysis will be described and fully documented in the SAP, which will be finalized prior to the start of the study. All statistical tests, between each risankizumab dose and placebo, will be performed at a two-sided alpha level of 0.025.

The statistical analyses will be performed using SAS (SAS Institute Inc., Cary, North Carolina, USA).

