## 7.3 Statistical Analyses for Efficacy

---

Analysis of all efficacy endpoints in Period A will be conducted on the ITT Population, based on treatment as randomized for Period A. In addition, the primary efficacy endpoint will be analyzed in the per-protocol population, if defined.

Comparison of the primary endpoint will be made between each risankizumab dose and placebo using the Cochran-Mantel-Haenszel (CMH) test, adjusting for stratification factors. Non-responder imputation (NRI) will be the primary approach to handle missing values. To account for impact of COVID-19 pandemic, the NRI will be adjusted to NRI-C, Non-Responder Imputation incorporating multiple imputation to handle missing data due to COVID-19.

The overall type-I error rate will be strongly controlled using a graphical multiple testing procedure. The primary and ranked secondary endpoints will be first tested in the ranked order specified in Section 3 between each risankizumab dose and placebo, with a 2-sided significance level of 0.025. Continued testing will follow a pre-specified  $\alpha$  transfer path which includes downstream transfer along the endpoint sequence. More details of the graphical procedure will be specified in the SAP.

Details on the primary and other efficacy analyses will be provided in the SAP.

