9.3.2 Main Analysis of Primary Efficacy Endpoint

The corresponding statistical null hypothesis to the primary endpoint is that there is no difference between each risankizumab dose and placebo, in the proportion of subjects achieving HiSCR at Week 16.

Comparison of the primary endpoint will be made between each risankizumab dose and placebo using the Cochran-Mantel-Haenszel (CMH) test, adjusting for the actual values stratification factors under a two-sided alpha level 0.025 for each dose.

The attributes of the estimand corresponding to the primary efficacy endpoint is summarized in Table 2.

Table 2. Summary of the Estimand Attributes of the Primary Efficacy Endpoint

	Attributes of the Estimand					
Estimand	Treatment	Endpoint	Population	Intercurrent Events	Statistical Summary	
Primary efficacy endpoint of HiSCR at Week 16	Risankizumab 180 mg / risankizumab 360 mg / Placebo	Achievement of HiSCR at Week 16 without the initiation of any antibiotics for HS-related infections and without discontinuation of study drug due to lack of efficacy	Patients with moderate to severe HS	The intercurrents of either initiation of any antibiotics for HS-related infections or discontinuation of study drug due to lack of efficacy are included in the endpoint attribute using composite variable strategy. No other intercurrent event is considered.	Difference in proportion of subjects achieving HiSCR at Week 16 between each risankizumab dose and placebo	

NRI-C will be the primary approach to handle missing data.

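### Does SAP 13.0 fall short of the graphical alpha-transfer procedure in protocol 7.3 because a dose that wins every test does not pass its 0.025 to the other dose?

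*SAP*

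**What the plan says.** Protocol 7.3 states: "The overall type-I error rate will be strongly controlled using a graphical multiple testing procedure". The primary and ranked secondary endpoints are first tested in order for each dose at two-sided 0.025. Then: "Continued testing will follow a pre-specified" alpha "transfer path which includes downstream transfer along the endpoint sequence". It closes with: "More details of the graphical procedure will be specified in the SAP".

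Protocol 7.1 fixes the level for every test: "All statistical tests, between each risankizumab dose and placebo, will be performed at a two-sided alpha level of 0.025". SAP 9.1 repeats this, and SAP 9.3.2 tests the primary endpoint "under a two-sided alpha level 0.025 for each dose".

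SAP 13.0 gives the operating rule. Within each dose, HiSCR comes first and the seven ranked secondaries follow, and each test opens only if the one above it was significant. The section says that "each comparison will be tested at a significance level of 0.025 and overall alpha level of 0.025 will be preserved for each risankizumab dose" and concludes that "the family-wised type-I error rate is controlled under a 2-sided significance level of 0.05". SAP 9.4.2 adds that the secondaries of a dose open only when that dose's own primary hypothesis has been rejected.

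**The concern.** A reader who comes from protocol 7.3 expects a graph with weights and arrows. The text of SAP 13.0 has neither, and the word graphical does not appear in it. The protocol says that the transfer path includes downstream transfer, which leaves room for other transfers. With two doses, the familiar extra arrow runs from the end of one dose's sequence to the first unrejected hypothesis of the other, which is then tested at 0.05.

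Without that arrow, some of the 0.05 can go unused. Suppose 360 mg wins HiSCR and all seven secondaries, and 180 mg has a HiSCR p-value between 0.025 and 0.05. Under SAP 13.0, 180 mg is not confirmed. With the arrow it would be, at the same family-wise bound. If the protocol had promised this, the SAP would have left it out, and a rule for reusing alpha cannot credibly be added after unblinding.

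**Working it through.** **1. Is the error rate controlled?** A false rejection within one dose requires rejecting the first true null hypothesis in its sequence, which is tested at 0.025. The error rate per dose is therefore at most 0.025, whatever the correlation among endpoints. For two doses it is at most 0.025 + 0.025 = 0.05, the SAP's own figure. Simulation with a shared placebo arm gives about 0.046 under the global null.

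**2. Is the rule a graphical procedure?** Yes. Put weight 1/2 on each dose's primary hypothesis and 0 on every secondary, so each primary starts at 0.05 × 1/2 = 0.025. Draw an arrow of weight 1 from each hypothesis to the next one in the same dose. A rejection then moves the whole 0.025 one step down. This is SAP 13.0, and it is the downstream transfer named in protocol 7.3.

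**3. Does either document provide for transfer between doses?** Not in its text. Such a transfer would create a test at 0.05, whereas protocol 7.1, SAP 9.1 and SAP 13.0 all fix 0.025 and SAP 9.3.2 does so for the primary endpoint. SAP 14.0 records that type-I error control was revised in SAP version 3.0 to align with the protocol, so the rule was revisited on purpose.

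**4. What would the extra arrow be worth?** Inputs from SAP Table 1: 74 per arm; placebo 26%; 360 mg 53%; 180 mg 39.5% (Linear), 46.5% (EMax) or 50% (early plateau). The method is exact enumeration of the three binomial counts, using a pooled z test with continuity correction because this variant comes close to the stated power.

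| | Linear | EMax | Early plateau |
|---|---|---|---|
| Power, at least one dose: stated | 83.9% | 87.6% | 90.6% |
| Power, at least one dose: enumerated | 84.5% | 88.0% | 91.0% |
| 360 mg power at 0.025 | 83.6% | 83.6% | 83.6% |
| 180 mg power at 0.025 | 25.0% | 57.2% | 72.9% |
| 180 mg power at 0.05 | 34.7% | 68.6% | 82.3% |
| Both confirmed on HiSCR under SAP 13.0 | 24.2% | 52.8% | 65.5% |
| Maximum gain from a 360-to-180 arrow (points) | 8.83 | 9.15 | 6.98 |

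The maximum gain is the sum, over placebo counts weighted by their probability, of P(360 mg rejected at 0.025) × [P(180 mg rejected at 0.05) − P(180 mg rejected at 0.025)]. It assumes that 360 mg wins all seven secondaries whenever it wins HiSCR. In general the gain is c × the maximum, where c is the probability of that clean sweep, taken as independent of the 180 mg result. The documents give no effect sizes for the secondaries, so c is assumed:

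| Assumed power per secondary; endpoint correlation | c | Gain in points (Linear / EMax / early plateau) |
|---|---|---|
| 60%; 0 | 0.028 | 0.2 / 0.3 / 0.2 |
| 60%; 0.3 | 0.14 | 1.2 / 1.3 / 1.0 |
| 80%; 0 | 0.21 | 1.9 / 1.9 / 1.5 |
| 80%; 0.3 | 0.40 | 3.5 / 3.7 / 2.8 |
| 80%; 0.6 | 0.57 | 5.0 / 5.2 / 4.0 |

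For example, Linear with c = 0.21: 0.21 × 8.83 = 1.9 points.

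**5. What would it cost?** SAP 13.0 bounds the chance of falsely confirming a null 180 mg dose at 0.025. With the arrow, simulation puts that chance at:
- 0.026 to 0.029 with independent secondaries at 60 to 80% power;
- 0.028 to 0.033 at correlation 0.3;
- 0.032 to 0.037 at correlation 0.6;
- 0.050 if 360 mg is effective on everything.

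The family-wise error stays at about 0.05 at most, but the separate bound per dose is lost.

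**The case for a change.** The best case for the concern has two parts.

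The first is wording. Protocol 7.3 says the endpoints are first tested in order at 0.025 and then speaks of continued testing. Once both sequences have been run, SAP 13.0 has no later stage. Together with the open word includes, this could lead a reader of the protocol to expect more than the SAP provides. That much stands: the two documents describe one rule in different terms, and a sentence saying that no alpha passes between doses would have been tidier. But the protocol defers to the SAP for the details, the SAP's rule can be applied in only one way, and rewording would change no test result.

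The second is efficiency. When one dose works on all eight endpoints and the other on none, the plan spends only 0.025 of its 0.05. An added arrow would fill the gap (simulated error 0.049 to 0.050) and would lose no rejection the SAP now makes. This is correct too. Yet SAP 13.0 expressly preserves 0.025 for each dose, and the arrow exchanges that property for a gain that arises only after eight straight wins. A sponsor's statistician can sensibly prefer either design.

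One limit applies: the text reviewed shows no graphics, and a figure marker stands in SAP 13.0. A graph with arrows between doses cannot be excluded, although the sentence fixing every comparison at 0.025 speaks against it. Such a graph would remove the premise of the concern.

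**Conclusion.** The concern does not hold. SAP 13.0 is a complete, valid rule with family-wise error at most 0.05. It performs the one transfer that protocol 7.3 names, and protocol 7.1, SAP 9.1, 9.3.2 and 9.4.2 are consistent with it. The stated objective (each dose against placebo) and the stated power (at least one dose) are unaffected.

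The option not taken is worth about 0.2 to 4 points in the probability of confirming both doses on HiSCR for endpoint correlations of 0 to 0.3, about 5 points at correlation 0.6 with 80% power per secondary, and 7.0 to 9.2 points at the ceiling. These figures rest on the planning rates, on assumed secondary power and correlation, and on transfer from 360 mg to 180 mg only; the reverse direction would add a little. They also depend on the test used. The planned CMH test has no stated continuity correction; without one, both doses are confirmed with probability 30.7/60.6/72.5% and the ceiling gain is 9.7/8.5/6.1 points. The conclusion is the same in either case: a design preference with a real price, not a fault in the plan.

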14.0 Version History

 Table 5.
 SAP Version History Summary

[figure not shown]
Version	Date	Summary		
1.0	7 Mar 2019	Original version		
2.0	26 Jul 2019	Added more statistical analysis details.		
3.0	08 Oct 2020	Removed section about RAR & IERC and updated the control for overall type-I error rate throughout the SAP, to align with the same updates after protocol version 3.0. Removed the stratification cap of TNF-IR population, to align with the same updates after protocol version 3.0. Clarified the definition of HiSCR and NRS30 throughout the SAP, to align with the updated wording after protocol version 3.0.		
ĺ		Clarified the timing and scope of the Primary Analysis.		
		Updated the details about how to handle subjects who do not continue into Period B from the ITT Population in Section 4.0, to align with the same updates after protocol version 3.0.		
		Updated the definition of concomitant medication in Section 7.3, to align with the most updated risankizumab PSSAP.		
		Clarified in Section 9.1 that the non-responder imputation (NRI) approach will be adjusted to NRI-C, Non-Responder Imputation incorporating multiple imputation to handle missing data due to COVID-19.		
		Added more details about handling missing data in Section 9.2 and Appendix E, including how to handle missing data caused by COVID-19 and subjects who received prohibited antibiotics or discontinued study drug to lack of efficacy.		
		Clarified shift tables, PCI, and ASI definitions for safety analysis in Section 10.0, Appendix B, Appendix C, and Appendix D, to align with the most updated risankizumab PSSAP.		
		Added estimands and their attributes for the primary endpoint and ranked secondary endpoints at Section 2.1, Section 8.0, Section 9.3, and Section 9.4.		

Version	Date	Summary
4.0	completion date for subjects who pre-maturely disco- participation during Period A in Section 6.0 and Sect	
		Corrected an error in Section 7.1, as PGIC does not apply at Baseline.
		Updated the definition of concomitant medication in Section 7.3, to align with the most updated risankizumab PSSAP.
		Included any adjudicated anaphylactic reaction to the AE overview table in Section 10.2.2 and Appendix B, to align with the most updated risankizumab PSSAP.
		Updated the lab test shift table categories and liver functioning test categories in Section 10.3 and added the reference to CTCAE version 4.03, to align with the most updated risankizumab PSSAP.

Appendix A. Protocol Deviations

The number and percentage of subjects who reported at least one of the following protocol deviation categories will be provided.

- Subject entered into the study even though s/he did not satisfy entry criteria.
- Subject developed withdrawal criteria during the study and was not withdrawn.
- Subject received wrong treatment or incorrect dose of study.
- Subject took prohibited concomitant medication.

Appendix B. Definition of Area of Safety Interest

Area of safety interest (ASI) will be identified using the following search criteria:

Area of Safety Interest		Include in AE Overview (Y/N)	
MACE		d terms will be identified as described in PSSAP Table 3 AT and CETERM from the CE SDTM dataset.	Y
Extended MACE		d terms will be identified as described in PSSAP Table 3 (+) using CECAT and CETERM from the CE SDTM	N
Serious Infections	Serious AE	s in the Infections and Infestations SOC	Y
Tuberculosis	Active Tub	erculosis CMQ (code 80000188)	Y
Opportunistic Infections	Opportunis CMQ (code	N	
Fungal Infections	Fungal infe	ections CMQ (code 80000063)	N
Herpes Zoster	Herpes Zos	ter CMQ (code 80000175)	Y
Malignant Tumours	Narrow	Malignant tumours (SMQ 20000194)	Y
Non-melanoma Skin Cancer (NMSC)	Broad	Skin malignant tumours (SMQ 20000204) excluding terms identified by the Melanoma CMQ (code 80000119)	N
Malignant Tumours excluding NMSC	'Malignant Tumours excluding NMSC' is identified by the 'Malignant Tumours' search excluding terms identified by the 'Non-melanoma skin cancer (NMSC)' search.		Y
Hypersensitivity	Narrow	Hypersensitivity (SMQ 20000214)	Y – serious events only
Adjudicated Anaphylactic Reaction*	Adjudicate PR domain	Y	
Hepatic Events	Broad	Hepatic failure, fibrosis and cirrhosis and other liver damage-related conditions (SMQ 20000013)	N
	Broad	Hepatitis, non-infectious (SMQ 20000010)	N
	Broad	Cholestasis and jaundice of hepatic origin (SMQ 20000009)	N
	Broad	Liver related investigations, signs and symptoms (SMQ 20000008)	N
	Narrow	Liver-related coagulation and bleeding disturbances (SMQ 20000015)	N

^{*} Events will be identified for adjudication by Anaphylactic Reaction SMQ Broad search as specified in the RISA AAC Charter.

Appendix C. Potentially Clinically Important Criteria for Safety Endpoints

The criteria for Potentially Clinically Important (PCI) laboratory findings are described in Table C-1 and Table C-2.

Table C-1. Criteria for Potentially Clinically Important Hematology Values

[figure not shown]
		Definition of Potentially Clinically Important: NCI CTCAE (Version 4) Grade 3 or Greater
Hematology Variables	Units	Very Low
Hemoglobin	g/dL	< 8.0
Platelets count	$10^{9}/L$	< 50.0
WBC count	$10^{9}/L$	< 2.0
Neutrophils	10 ⁹ /L	< 1.0
Lymphocytes	10 ⁹ /L	< 0.5

Note: A post-baseline grade must be more extreme than the baseline grade to be considered a potentially clinically important finding.

Table C-2. Criteria for Potentially Clinically Important Chemistry Values

[figure not shown]
		Definition of Potentially Clinically Important: NCI CTCAE (Version 4) Grade 3 or Greater	
Chemistry Variables	Units	Very Low	Very High
TBL	mcmol/L		> 3.0 × ULN
ALP	U/L		$> 5.0 \times ULN$
SGOT/AST	U/L		$> 5.0 \times ULN$
SGPT/ALT	U/L		$> 5.0 \times ULN$
Albumin	g/L	< 20	
Glucose	mmol/L	< 2.2	> 13.9
Triglycerides	mmol/L		> 5.7
Creatinine	mcmol/L		$>$ 3.0 \times ULN or $>$ 3.0 \times baseline
Sodium	mmol/L	< 130	> 155
Potassium	mmol/L	< 3.0	> 6.0
Calcium	mmol/L	< 1.75	> 3.1
CPK	U/L		$> 5.0 \times ULN$
Total Cholesterol	mmol/L		> 10.34
GGT			> 5.0 × ULN

Note: A post-baseline grade must be more extreme than the baseline grade to be considered a potentially clinically important finding.

